8.4. Sample size and power

The number of pregnant women enrolled and the number of study participants reaching the various endpoints will determine the sample sizes for each of the primary outcomes of our study aims (Table 9). The primary determinant of our target sample size was based on testing hypotheses 3 given that the magnitude of differences anticipated for this hypothesis would be smaller than those anticipated for hypothesis 1 and 2. We conservatively estimate that 90% of pregnant women enrolled will reach the primary study endpoint and we will lose 5% of follow-up time per year in the infants. The minimum relative differences detectable for the primary outcomes of the 3 hypotheses given our estimated sample sizes are summarized in Table 10 below. For hypotheses 1, we will be powered to detect a 33% relative difference in the prevalence of placental malaria in the 3 dose DP arm or the monthly DP arm compared to the 3 dose SP arm assuming a prevalence of placental malaria of 62% in the 3 dose SP arm based on prior data. We will also be powered to detect a 41-70% relative difference in the prevalence of placental malaria in the monthly DP arm compared to the 3 dose DP arm assuming a prevalence of placental malaria in the 3 dose DP arm ranging from 20-50%. For hypothesis 2, we will be powered to detect an 18-23% relative difference in the incidence of malaria between 0-24 months of age in the monthly DP arm compared to the q 3 monthly DP arm assuming an incidence of malaria in the q 3 monthly DP arm ranging from 3-5 episodes PPY. For hypothesis 3A, we will be powered to detect a 22-28% relative difference in the incidence of malaria between 0-24 months of age among children assigned to receive q 3 monthly DP when comparing those born to mothers who received 3 dose SP to those born to mothers who received 3 dose DP or monthly DP assuming an incidence of malaria in the control group ranging from 3-5 episodes PPY. For hypothesis 3B, we will also be powered to detect a 16-21% relative difference in the incidence of malaria between 24-36 months of age among children assigned to receive monthly DP during infancy compared to those who received q 3 monthly DP

during infancy assuming an incidence of malaria in the control group ranging from 3-5 episodes PPY.

Table 9. Intervention arms during pregnancy and infancy

Study populations	Intervention arms				
	3 doses of SP	3 doses of DP		monthly DP	
Assigned treatment arms in pregnant women	3 doses of SP	3 doses of DP		monthly DP	
Estimated number of pregnant women enrolled	100	100		100	
Estimated number with placental outcomes	90	90		90	
Assigned treatment arms in infants	q 3 monthly DP	q 3 monthly DP	monthly DP	q 3 monthly DP	monthly DP
Estimated number of infants enrolled	90	45	45	45	45
Estimated number of infants reaching 24 months of age	81	41	41	41	41

Table 10. Minimum relative differences in outcomes detectable given estimated effective sample sizes

Hypothesis	Analysis population	Control group and estimated sample size	Comparison group and estimated sample size	Estimated outcome measure in control group	Minimum relative difference detectable*
1	Pregnant women with placental malaria measured at birth	3 dose SP (n=90)	3 dose DP or monthly DP (n=90 each)	Prevalence of placental malaria = 62%	33%
		3 dose DP (n=90)	monthly DP (n=90)	Prevalence of placental malaria = 20-50%	41-70%
2	Infants 0-24 months of age born to mothers assigned to receive IPTp with 3 dose DP or monthly DP	Infants assigned q 3 monthly DP (n=90)	Infants assigned monthly DP (n=90)	Incidence of malaria = 3-5 episode PPY	18-23%
3	Infants 0-24 months of age randomized to q 3 monthly DP	Infants of mothers assigned 3 dose SP (n=90)	Infants of mothers assigned 3 dose DP or monthly DP (n=45 each)	Incidence of malaria = 3-5 episodes PPY	22-28%
	Infants 24-36 months of age after chemoprevention stopped	Infants assigned q 3 monthly DP (n=162)	Infants assigned monthly DP (n=81)	Incidence of malaria = 3-5 episodes PPY	16-21%

* Relative difference = (estimated outcome in control arm – estimated outcome in the comparison arm) / estimated outcome on the control arm (two-sided alpha = 0.05, power = 80%).

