In all 4 arms the incidence of malaria increased with age (Figure 3), and the protective efficacies of all 3 interventions decreased over the course of the study. Supporting pharmacokinetic data suggests that the majority of children randomized to DP were not compliant with their regimen at the times they were diagnosed with malaria. Another finding of interest was that the incidence of malaria was over 5 episodes per year in children 4-5 months of age prior to randomization, suggesting the need to begin chemoprevention earlier than 6 months of age as was done in this study.

Figure 3. Incidence of malaria over age stratified by assigned treatment arm

Data are also available for the one year period following the completion of the intervention (Table 2). Of 352 children who reached 24 months of age when chemoprevention was stopped; 340 reached 36 months of age and completed the study and 12 were withdrawn before reaching 36 months of age. The incidence of malaria was very high after stopping chemoprevention, reaching almost 11 episodes per year at risk. Importantly, these data do not show a “rebound” of increased malaria after completion of chemoprevention. For all arms,

there has been no significant difference in the incidence of malaria following chemoprevention compared to the control group.

Table 2. Incidence of malaria following cessation of chemoprevention

Treatment arm	24-36 months of age				
	Number of cases	PYAR	Incidence per PYAR	IRR (95% CI)	p value
No prior therapy	670	61.8	10.85	1.0 (reference)	-
Prior Monthly SP	689	57.5	11.98	1.11 (0.88-1.40)	0.37
Prior Daily TS	678	62.2	10.90	1.01 (0.80-1.27)	0.95
Prior Monthly DP	659	61.2	10.77	0.99 (0.79-1.25)	0.96

PYAR=person years at risk; IRR = incidence rate ratio

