8.1.3. Analyses

An intention-to-treat approach to all analyses will be used, including all study participants randomized to therapy and including all follow-up time until the study participants complete the study or early study termination regardless of whether the intervention was stopped due to an adverse event.

Primary analysis. We will compare the prevalence of placental malaria defined by histopathology at birth between the study arms using the Chi-Square test for all pair-wise comparisons. We will explore for any differences of potential confounders between the treatment arms and if necessary adjust our analysis using multivariate logistic regression.

Secondary analyses. We will compare the prevalence of placental parasitemia and our composite birth outcome using the Chi-Square test. We will compare the incidence of maternal malaria and adverse events using Poisson or negative binomial regression models. The Poisson models will include the logarithm of the follow-up time as an offset. We will translate the fitted coefficients and their confidence bounds into percentage effects with the formula $100 * [\exp(\text{coefficient}) - 1]$. This approach is closely related to exponential survival models for analyzing events per follow-up time, but is better able to adjust for violated assumptions. Testing for overdispersion in the Poisson regression can detect violations of these assumptions, and variances can be adjusted accordingly to produce valid p-values and confidence interval. If significant deviations from required distributions in study data are detected, we will employ negative-binomial or zero-inflated negative-binomial models to account for the observed pattern of data. We will compare the prevalence of maternal anemia and asymptomatic parasitemia using generalized estimating equations with adjustments for repeated measures in the same study participant. If necessary, multivariate analyses will be performed to adjust for potential confounders and effect modifiers.

8.2. Hypothesis 2

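### The 80%-power detectable differences for hypotheses 2, 3A and 3B rest on Poisson variance, which the protocol's own preliminary data contradict; power at those differences is well below 80%, most clearly for 3B.

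*Protocol*

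**What the plan says.** Section 8.4 and Table 10 give minimum detectable relative differences at "two-sided alpha = 0.05, power = 80" per cent.

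- Hypothesis 2 (90 vs 90 infants): "we will be powered to detect an 18-23% relative difference in the incidence of malaria between 0-24 months of age", "assuming an incidence of malaria in the q 3 monthly DP arm ranging from 3-5 episodes PPY".
- Hypothesis 3A (90 vs 45): "we will be powered to detect a 22-28% relative difference in the incidence of malaria between 0-24 months of age", over the same range of control incidence.
- Hypothesis 3B (162 vs 81): "we will also be powered to detect a 16-21% relative difference in the incidence of malaria between 24-36 months of age", again at 3-5 episodes per person-year.

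The inputs shown are sample size, control incidence, alpha and power. No dispersion parameter, standard deviation or design effect is given. The same section says: "The primary determinant of our target sample size was based on testing hypotheses 3".

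Time at risk is birth to 24 months for hypotheses 2 and 3A and 24 to 36 months for 3B (sections 8.2.1 and 8.3.1). Section 8.4 allows for losing 5% of infant follow-up time per year. For the analysis, section 8.1.3 provides that if the data depart from the required distributions, "we will employ negative-binomial or zero-inflated negative-binomial models to account for the observed pattern of data". Sections 8.2.3 and 8.3.3 refer back to that method.

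**The concern.** Malaria episodes cluster in some children, so counts per child usually vary more than a Poisson distribution allows. Section 8.1.3 foresees this for the analysis, but section 8.4 does not carry it into the power statement. The protocol already holds evidence on its size: Tables 1 and 2 of section 1.2 report case counts with confidence intervals from the same group's trial in the same town. In Table 2, for instance, the rate ratio for prior monthly SP is "1.11 (0.88-1.40"), which is wide for 689 cases against 670.

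If the variance is understated, so are the detectable differences. This matters most for hypothesis 3, which set the sample size. A non-significant result there could be taken as evidence against effects that the trial had less than an even chance of detecting.

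**Working it through.** **1. Reproducing Table 10.** For a control rate r, relative difference d, r2 = r(1-d), and t person-years per child, a two-rate test with Poisson variance solves

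r - r2 = 1.96·sqrt[(pooled rate/t)(1/n1 + 1/n2)] + 0.8416·sqrt[r/(n1·t) + r2/(n2·t)].

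| Hypothesis | n | Stated at 3 / 5 per PY | Poisson, t = 1 |
|---|---|---|---|
| 2 | 90 vs 90 | 23% / 18% | 22.7% / 17.8% |
| 3A | 90 vs 45 | 28% / 22% | 27.7% / 21.8% |
| 3B | 162 vs 81 | 21% / 16% | 21.0% / 16.4% |

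All six end-points match after rounding. With t = 1.9 (two years less 5%), Poisson variance on the log-rate scale gives 16.8% / 13.1% for hypothesis 2 and 20.7% / 16.2% for 3A, so the stated figures use one person-year.

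**2. Dispersion in the preliminary data.** SE from the interval = ln(upper/lower)/3.92. Poisson SE = sqrt(1/cases1 + 1/cases2). The variance ratio is the square of their quotient. Then k = (SE² - 1/cases1 - 1/cases2)/(2/n), with n = 393/4 ≈ 98 per arm (Table 1) and 352/4 = 88 (Table 2).

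| Comparison with control | Cases | SE from CI | Poisson SE | Variance ratio | k |
|---|---|---|---|---|---|
| SP, 6-24 mo | 725 vs 760 | 0.128 | 0.052 | 6.1 | 0.67 |
| TS, 6-24 mo | 609 vs 760 | 0.129 | 0.054 | 5.7 | 0.68 |
| DP, 6-24 mo | 366 vs 760 | 0.130 | 0.064 | 4.2 | 0.63 |
| SP, 24-36 mo | 689 vs 670 | 0.118 | 0.054 | 4.8 | 0.49 |
| TS, 24-36 mo | 678 vs 670 | 0.118 | 0.054 | 4.7 | 0.48 |
| DP, 24-36 mo | 659 vs 670 | 0.117 | 0.055 | 4.6 | 0.47 |

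First row: ln(1.19/0.72)/3.92 = 0.128; sqrt(1/760 + 1/725) = 0.052. The variance ratio does not depend on arm size; k does.

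**3. Power at the stated differences.** With negative binomial variance,

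SE² = 1/(r·n1·t) + 1/(r(1-d)·n2·t) + k(1/n1 + 1/n2), and power = Φ(-ln(1-d)/SE - 1.96).

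Example, 3B at 3 per person-year, d = 0.21, t = 1, k = 0.5: SE² = 0.00206 + 0.00521 + 0.00926 = 0.01653, so SE = 0.1286. Power = Φ(0.2357/0.1286 - 1.96) = Φ(-0.13) = 45%.

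| Hypothesis (t) | Control rate | Stated d | k = 0 | k = 0.25 | k = 0.5 | k = 0.7 |
|---|---|---|---|---|---|---|
| 2 (1.9) | 3 | 23% | 97% | 74% | 55% | 45% |
| 2 (1.9) | 5 | 18% | 97% | 59% | 40% | 31% |
| 3A (1.9) | 3 | 28% | 97% | 75% | 56% | 47% |
| 3A (1.9) | 5 | 22% | 97% | 60% | 41% | 32% |
| 3B (1.0) | 3 | 21% | 79% | 58% | 45% | 38% |
| 3B (1.0) | 5 | 16% | 77% | 46% | 32% | 26% |

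Simulated negative binomial counts at k of 0.47 and 0.68 agree with this formula within about 4 points.

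**4. How much dispersion the stated figures tolerate.** Setting power to 80% and solving for k gives at most 0.19 (3 per person-year) or 0.11 (5 per person-year) for hypotheses 2 and 3A, a variance inflation of 1.9. For 3B the solution is slightly below zero, so there is no room at all.

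**5. Detectable differences at 80% power.** Solving -ln(1-d) = 2.8016·SE over 3-5 per person-year:

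| Hypothesis | Stated | k = 0.25 | k = 0.5-0.7 |
|---|---|---|---|
| 2 | 18-23% | 22-25% | 28-33% |
| 3A | 22-28% | 27-30% | 34-39% |
| 3B (162 vs 81) | 16-21% | 23-27% | 28-34% |

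**The case against.** The strongest reply is that k is inferred. The protocol does not state the model behind Tables 1 and 2, and the reported efficacies differ slightly from the crude rate ratios: for SP, 1 - 6.73/6.95 = 3% against 7% reported. Equal arm sizes are assumed. The earlier trial was open-label, began treatment at 6 months and gave drugs at home unsupervised, whereas this one follows a birth cohort with the first daily dose observed in clinic. This stands as a reason to use a range of k rather than one value. It does not restore the stated power: all six comparisons agree closely, and k of 0.25, about half or less of any observed value, still leaves every row below 80%.

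Four stronger readings are tempting, and the documents do not support them.

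- A reader might infer that the one-person-year input is a second error that worsens the first. For hypotheses 2 and 3A it is conservative: Poisson variance over 1.9 person-years gives 97% power. It partly offsets the omission, though by too little.
- A reader might infer that the stated differences are out of reach at any incidence. That depends on k. At k = 0.25 the limits as incidence grows without bound are 18.8%, 22.6% and 17.4% for hypotheses 2, 3A and 3B, below the stated upper ends of 23%, 28% and 21%.
- A reader might apply the 4.2-6.1 ratio directly to 3B. The ratio grows with the mean count per child, and Table 2 reflects about 11 episodes per person-year. At 3-5 per person-year and k of 0.5-0.7, the inflation for 3B is about 2.2-4.0.
- A reader might infer that the analysis itself is invalid. Section 8.1.3 already tests for overdispersion and allows negative binomial models, so type I error is protected if that provision is followed. The defect is in the power statement.

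**Conclusion.** The point holds for the power statement. Section 8.4 and Table 10 claim 80% power at differences that need Poisson variance, while the protocol's own tables imply k of about 0.63-0.68 (6-24 months) and 0.47-0.49 (24-36 months). With k of 0.5-0.7, power at the stated differences is about 31-56% for hypotheses 2 and 3A and 26-45% for 3B. Hypothesis 3B is the clearest case, because one year is its actual time at risk and no unused follow-up offsets the missing variance; it is also part of the hypothesis that fixed the sample size.

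This rests on k back-calculated from published intervals under equal arm sizes and an unstated model, on about 1.9 person-years per child for hypotheses 2 and 3A and one for 3B, and on the protocol's control rates and sample sizes. Hypothesis 1 is unaffected. Hypothesis 2 could still be adequately powered if the true difference exceeds about 33%.

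**What to change.** Restate the hypothesis 2, 3A and 3B rows of Table 10 and the matching text of section 8.4 using negative binomial variance, the actual person-time for each hypothesis, and a stated range of k with its source in Tables 1 and 2. Show k of 0.5-0.7 as the range suggested by the preliminary data and k of 0.25 as a favourable sensitivity case, with the detectable differences in step 5 of the working. If the sponsor can reach the preliminary trial's individual data, k can be estimated directly instead of back-calculated.

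The cost is a less favourable set of figures; no added enrolment or data collection is needed. Two further changes are not part of this fix. Section 8.3.3 includes all infants who reach 24 months in 3B, so the 162 vs 81 comparison should be kept here. Nor does this point require fixing one primary model, since section 8.1.3 already provides for negative binomial regression.

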8.3.1. Primary Outcome

The primary outcome will be the incidence of malaria, defined as the number of incident episodes per time at risk. Incident cases will include all treatments for malaria not preceded by another treatment in the previous 14 days. For hypothesis 3A, time at risk will begin at birth and will end when study participants reaches 24 months of age or early study termination (if prior to 24 months of age). For hypothesis 3B, time at risk will begin at 24 months of age and will end when study participants reaches 36 months of age or early study termination (if between 24-36 months of age).

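### Hypothesis 3B is sized on an unsourced 3-5 episodes per person-year at 24-36 months with no dispersion allowance; on the protocol's own Table 2 data the detectable difference is about 25-26%, not 16-21%.

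*Protocol*

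**What the plan says.** Protocol section 8.4 says of hypothesis 3B that the trial is "powered to detect a 16-21% relative difference in the incidence of malaria between 24-36 months of age", "during infancy assuming an incidence of malaria in the control group ranging from 3-5 episodes PPY". The last row of Table 10 gives the group sizes as "Infants assigned q 3 monthly DP (n=162") and "Infants assigned monthly DP (n=81"), and the table footnote sets "two-sided alpha = 0.05, power = 80" per cent. Section 8.3.1 defines the 3B period: "time at risk will begin at 24 months of age and will end when study participants reaches 36 months of age", or early termination. Section 8.4 uses the same 3-5 range for the 0-24 month comparisons (hypotheses 2 and 3A). It also states: "The primary determinant of our target sample size was based on testing hypotheses 3".

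Section 1.2 reports the sponsor's earlier Tororo trial over the same age window after chemoprevention ended: "The incidence of malaria was very high after stopping chemoprevention, reaching almost 11 episodes per year at risk". By prior arm, Table 2 gives 10.85 (no therapy), 11.98 (monthly SP), 10.90 (daily TS) and 10.77 (monthly DP) episodes per person-year at risk.

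**The concern.** One range, 3-5 episodes per person-year, serves both infants on active DP and children who have stopped it. During monthly DP at 6-24 months, Table 1 shows 3.02, so 3-5 is plausible on treatment. At 24-36 months off treatment, all four Table 2 arms are near 11. Section 8.4 cites prior data for the placental malaria prevalence but gives no source for this incidence.

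Table 2 also shows how variable these counts are between children. Its confidence intervals are far wider than Poisson variation allows, and the 3B calculation contains no allowance for that.

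Hypothesis 3 is named as the main driver of the sample size. Someone using Table 10 to see how small an effect 3B can reliably detect is given a figure that does not describe the population the protocol's own data predict.

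**Working it through.** **Inputs.** Section 8.4 and Table 10: 162 and 81 children, two-sided alpha 0.05, power 80%, control rate 3-5. Section 8.3.1: one year per child. z(0.975) + z(0.80) = 1.960 + 0.842 = 2.802.

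**1. Reproducing 16-21%.** For two Poisson rates with control rate L, solve for the relative difference r:

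L·r / √(L/162 + L(1−r)/81) = 2.802

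- L = 3: r = 20.5%. Check: 0.615/√(0.01852 + 0.02944) = 2.81.
- L = 5: r = 16.1%. Check: 0.805/√(0.03086 + 0.05179) = 2.80.

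The stated range follows from its inputs, as a pure Poisson calculation. Log-scale and pooled-variance versions give 21.0-21.3% and 16.4-16.6%.

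**2. Putting Table 2 on the 8.3.1 time scale.** Table 2 totals 670 + 689 + 678 + 659 = 2,696 cases over 61.8 + 57.5 + 62.2 + 61.2 = 242.7 person-years at risk, in 352 children who reached 24 months.

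- Cases per child: 2,696/352 = 7.66.
- Person-years at risk per child: 242.7/352 = 0.69.
- Adding 14 days per case: 0.69 + 7.66 × 14/365 = 0.98 year.

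This suggests that Table 2 excludes about 14 days after each episode. That is an inference, because the protocol does not define its person-years at risk. Section 8.3.1 states no such exclusion. On a full-time basis the rate is 7.66/0.98 = 7.8 per child-year, still above 3-5.

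**3. Correcting the rate only (Poisson, formula in step 1).**

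- L = 7.8: r = 13.0%; power for a 16% difference is 93%.
- L = 10.8: r = 11.2%; power for a 16% difference is 98%.
- For comparison, at L = 3 and 5 the power for 16% is 58% and 79%.

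**4. Dispersion implied by Table 2.** For prior monthly DP against no prior therapy, the interval 0.79-1.25 gives SE(log IRR) = ln(1.25/0.79)/3.92 = 0.117. The Poisson SE is √(1/659 + 1/670) = 0.0549. Variance inflation is (0.117/0.0549)² ≈ 4.6. The three comparisons give 4.55 to 4.77.

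Under a negative binomial model, inflation = 1 + k × (mean events per child), so k = (4.55 − 1)/7.66 = 0.46. Working directly from the SE with about 88 children per arm (352/4, an assumed even split) gives 0.47 to 0.49. I use k = 0.47.

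**5. Rate and dispersion together.** Solve

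−ln(1−r) / √[(1/L + k)/162 + (1/(L(1−r)) + k)/81] = 2.802

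| Control rate L | Poisson (step 1 formula) | Negative binomial, k = 0.47 | Power for 21%, k = 0.47 |
|---|---|---|---|
| 3 | 20.5% | 30% | 46% |
| 5 | 16.1% | 28% | 54% |
| 7.8 | 13.0% | 26% | 59% |
| 10.8 | 11.2% | 25% | 62% |

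At 10.8, varying k from 0.3 to 0.5 moves the detectable difference from about 22% to 26%.

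**The case against.** Several points on the other side stand.

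- A reader might infer that 16-21% is a calculation error. It is not: it reproduces from its stated inputs and is expressly conditional on 3-5 episodes.
- A reader might infer that the low control rate leaves 3B underpowered. The documents do not support that. Under the Poisson method that reproduces the figure, a higher rate shrinks the detectable difference, so the rate assumption taken alone is conservative. The optimism comes from leaving out between-child variation.
- A reader might infer that 3B fixed the sample size. Section 8.4 names hypothesis 3 as a whole. Hypothesis 3A has smaller groups (90 against 45 each) and a larger stated detectable difference (22-28%).
- The figure of about 11 should not be multiplied by full child-years, because Table 2 counts only about 0.69 year at risk per child. The like-for-like gap is about 1.6- to 2.6-fold (7.8/5 to 7.8/3).
- Table 2 is not the identical population. No arm received 3-monthly DP, and dosing began at 6 months, unsupervised at home. In this trial dosing begins at 2 months, with the first daily dose observed.
- A null 3B result will be read from its confidence interval, not from Table 10. The planned analysis already allows negative binomial models, so the final inference is not at risk.

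None of this supplies a source for 3-5 episodes at 24-36 months. The difference in prior regimen is also a weak defence, since rates after no therapy, SP, TS and DP all fell between 10.77 and 11.98.

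**Conclusion.** The point holds as an inconsistency between planning inputs and the protocol's own data. The 3-5 range for 24-36 months is unsourced and lies below Table 2 on either time scale. The 16-21% also needs counts with no extra-Poisson variation, whereas Table 2 implies a variance about 4.6 times Poisson. With the Table 2 rate, the detectable difference is about 11-13% under Poisson and about 25-26% with dispersion; the second is the realistic one. Even at the protocol's own 3-5 episodes, dispersion alone raises it to about 28-30%.

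This rests on four assumptions: the Table 2 intervals are symmetric on the log scale; the 352 children split about evenly; dispersion in this trial resembles that of the earlier one; and each child contributes one year. The full-time rate of 7.7-7.8 is inferred. The conclusion is not sensitive to it, because with k = 0.47 the result moves only from 26% to 25% between 7.8 and 10.8.

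**What to change.** In section 8.4 and the last row of Table 10:

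1. Replace 3-5 episodes for the 24-36 month comparison with a Table 2-based rate on the time-at-risk definition of section 8.3.1, and cite the table. A range of 5-11 is one example; it covers both time scales and leaves room for a lower rate than before.
2. In the same calculation, apply the dispersion implied by Table 2 (about 0.47) and state it.
3. Restate the detectable difference, which is about 25-28% over 5-11 episodes.

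The rate and the dispersion should change together. Changing the rate alone would print about 11-13%, further from the realistic figure than the present text.

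The cost is one table row, one sentence and a less favourable stated figure. Conduct and enrolment do not change.
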